2.8.2.3 Cross-sectional analysis

The mean and standard deviation of QOL scores at baseline and mean and standard deviation of QOL change scores from baseline at each assessment time will be calculated.

Summary statistics of baseline score for each domain in FACT-HN and MDADI will be summarized in Table 19. Mean QOL change score from baseline for each assessment time will be summarized in Table 20.

2.8.3 Analysis of FOIS and PSS-HN.

FOIS and PSS-HN are not a patient reported outcome however it is an important investigator-completed assessment of swallowing function and have been included in HN10. “Compliance” does not apply, and MID is not well defined for FOIS and PSS-HN. Thus, only the cross-sectional analysis specified in 2.8.2.3 will be conducted for both.

Cross-sectional analysis results related to FOIS and PSS-HN will be summarized in Table 21.

Figure 1. KM for EFS

Figure 2. KM for OS

Figure 3. KM for LRC

Figure 4. KM for out-of-field regional control

Figure 5. KM for DMFS

Figure 6. Boxplots for FACT domain score changes from baseline by assessment time

Figure 7. Boxplots for MDADI domain score changes from baseline by assessment time

Figure 8. Boxplots for FOIS domain score changes from baseline by assessment time

Figure 9. Boxplots for PSS-HN domain score changes from baseline by assessment time

Table 1. Accrual by center

Data set: All Patients

	Number of patients (%)	
	Total N = ***	
Canada	*** (**)	
Center #1	*** (**)	
Center #2	*** (**)	
...	*** (**)	
...		

Table 2. Eligibility and reasons for ineligibility

Data set: All Patients

	Number of patients (%)	
	Total N = ***	
Eligible/Evaluable	*** (**)	
Not Eligible/Inevaluable	*** (**)	
Major protocol violation		**
<violation type 1>		**
<violation type 2>		
...		

Table 3. Baseline patient characteristics

Data set: All Patients (N = 103)	
	Total N = 103
Age (years)	
N	
Median (Min-Max, Q1-Q3)	
Mean (SD)	
≥ 65	
<65	
Sex	
Female	
Male	
ECOG Performance Status	
0	
1	
T Stage	
T1	
T2	
T3	
T4 ¹	
N Stage	
N0	
N1	
N2 ²	
Primary site	
Base of tongue	

Tonsil	
Soft palate	
Smoking history	
No smoking ever	
Smoked ever	
Greater than 100 cigarettes during lifetime	
100 or fewer cigarettes during lifetime	
Pipe or cigar smoker only	
Length of smoking in years	
N	
Median (Min-Max, Q1-Q3)	
Mean (SD)	
Current smoking	
Yes	
No	
Unknown or not answered	
Current average number of cigarettes smoked per day	
N	
Median (Min-Max, Q1-Q3)	
Mean (SD)	

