EQ-5D-5L Questionnaire	
 • Prior to registration • Last week of radiotherapy • After RT (prior to PD): 3, 6, 12, 24 and 36 months 	On paper; site CRA to enter relevant data (as required) in the EDC system within corresponding folders	Retain questionnaires at the site
MDADI			
PRO-CTCAE			
Lost Productivity Questionnaire	
 • During the last week of RT • After RT (prior to PD): 6 and 12 months 		

* See Appendices V, VI, VII and VIII. If the questionnaire is completed on paper then it should be scanned and uploaded to the EDC Supporting Document Upload Tool.
			

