1.2 Sample size and power

The 2-year EFS was estimated to be 91% (Ha) for low-risk HPV-related OPSCC. Assuming that the experimental treatment will be considered as ineffective if the 2-year EFS is $\leq 85\%$ (H0), with one-sided alpha of 0.1, a sample size of 100 patients will have 80% power to detect a 6% difference of 2-year EFS. With 3 years of accrual and 2 years of follow-up, the total duration of this study will be 5 years. A total of 304.7 person-years of follow-up is needed for the final analysis. The null hypothesis (H0) will be rejected when the observed survival rate is 88.85% or higher (i.e. if there are 18 or fewer EFS events observed).

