1.3 Timeline

The analysis will include data accumulated until May 31, 2024 (estimated timing, specific timing decided until 304.7 person-years of follow-up are observed).

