2.8.2 Analysis

All analyses on quality-of-life scores will include all eligible patients who have a measurement at baseline and at least one measurement after baseline.

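### Quality-of-life and swallowing change scores are summarised only as available-form means, so the month-36 mean will describe a smaller, earlier-enrolled, progression-free subset of the month-24 patients

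*SAP*

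**What the plan says.** SAP 2.8.2.3 is headed as a cross-sectional analysis. It states that the "mean and standard deviation of QOL change scores from baseline at each assessment time will be calculated", and then: "Mean QOL change score from baseline for each assessment time will be summarized in Table 20". Boxplots by assessment time go with it (Figures 6 and 7). For FOIS and PSS-HN, SAP 2.8.3 says that "only the cross-sectional analysis specified in 2.8.2.3 will be conducted for both" (Table 21, Figures 8 and 9).

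Under SAP 2.8.2, a patient enters the analysis with a form "at baseline and at least one measurement after baseline". A form at every time is not required. No model, fixed cohort, confidence interval or missing-data method is given for these scores. Protocol 13.6 likewise plans descriptive statistics only.

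Three other passages decide who can contribute at each time:

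- **Cut-off.** SAP 1.3 says "The analysis will include data accumulated until May 31, 2024", an estimate that moves to when 304.7 person-years have been observed.
- **Schedule.** Protocol Appendix III lists the questionnaires as "After RT (prior to PD): 3, 6, 12, 24 and 36 months". The flowsheet in Protocol 5.0 places the follow-up QOL, FOIS and PSS-HN assessments in the column that runs until recurrence or progression.
- **Window.** SAP 2.8.2.1 counts a form as month 36 if it falls from 30 to under 42 months after the off-treatment date. The month-24 window is 18 to under 30 months.

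**The concern.** Tables 20 and 21 and Figures 6 to 9 line the time points up side by side, and readers will take them as a course of recovery. The contributing set shrinks along that course for two reasons. Late-enrolled patients will not have reached month 36 at the cut-off, and patients who progress or die stop contributing. A difference between the month-24 and month-36 means can therefore reflect change within patients, a change in who contributes, or both. The plan has no summary that separates them.

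Reducing toxicity and improving QOL is the stated rationale for reducing the nodal volume (Protocol 2.0), and swallowing and QOL are secondary objectives. Protocol 2.0 also suggests that the long-term effect on QOL settles by about 2 years. Months 24 and 36 are the visits that could show whether it does.

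**Working it through.** **Inputs**

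- Planned calendar: "With 3 years of accrual and 2 years of follow-up, the total duration of this study will be 5 years" (SAP 1.2), so accrual A = 36 months and cut-off T = 60 months.
- Trigger: 304.7 person-years (SAP 1.2 and 1.3).
- Patients: 103 enrolled, 99 eligible (SAP 1.6).
- 2-year EFS: 85% (H0) and 91% (Ha).
- Lag from registration to end of RT: up to 3 weeks to start (Protocol 7.0) plus 6 to 7 weeks of RT (Protocol 7.2), about 1.4 to 2.3 months. I use 2 months.
- Assumptions: uniform accrual and exponential EFS.

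**Step 1. Reproduce the plan's figures.** With λ = −ln(2-year EFS)/2 per year and times in years, expected person-years are (N/A) × ∫ (1 − exp(−λ(T − u)))/λ du over entry times u from 0 to A. For N = 100, A = 3, T = 5 this gives 302.3 under H0, within 1% of 304.7, and 321.1 under Ha. The decision rule also agrees: exp(−2 × 18/304.7) = 0.8886, against the stated 88.85%.

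**Step 2. Share reaching a visit on the planned calendar.** Share = (T − visit month − lag)/A, in months, capped at 1.

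- Month 24: (60 − 24 − 2)/36 = 94%
- Month 36: (60 − 36 − 2)/36 = 61%

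**Step 3. Let the person-year trigger set the cut-off.** I solved the Step 1 formula for the T that gives 304.7 person-years, then applied the Step 2 formula. The last column is the share at which the SAP's month-36 window has opened (30 months).

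| 2-year EFS | N | Accrual (months) | T (months) | Month 24 | Month 36 | Window open |
|---|---|---|---|---|---|---|
| 85% | 99 | 24 | 54.7 | 100% | 69% | 94% |
| 85% | 99 | 36 | 60.9 | 97% | 64% | 80% |
| 85% | 103 | 24 | 52.8 | 100% | 62% | 87% |
| 85% | 103 | 36 | 59.0 | 92% | 58% | 75% |
| 91% | 99 | 24 | 52.0 | 100% | 58% | 83% |
| 91% | 99 | 36 | 58.1 | 89% | 56% | 73% |
| 91% | 103 | 24 | 50.3 | 100% | 51% | 76% |
| 91% | 103 | 36 | 56.4 | 85% | 51% | 68% |

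The ranges are 85–100% at month 24, 51–69% at nominal month 36, and 68–94% for the month-36 window.

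**Step 4. Remove patients with EFS events.** EFS serves as a proxy for forms stopping at progression or death. The event-free share at registration + 26 months (month 24) is 0.85^(26/24) = 0.839 or 0.91^(26/24) = 0.903. At registration + 38 months (month 36) it is 0.85^(38/24) = 0.773 or 0.91^(38/24) = 0.861. Multiplying row by row gives 76–90% at month 24 (lowest 0.846 × 0.903, highest 1.00 × 0.903). At month 36 it gives 44–54% (lowest 0.512 × 0.861, highest 0.694 × 0.773).

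In every row the month-36 group is clearly smaller than the month-24 group.

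**The case against.** The strongest reply is that the analysis claims little. It is labelled cross-sectional, follows the protocol's descriptive intent, and plans no test between visits. Tables 20 and 21 print N at each time and Table 18 prints forms received over expected, so the falling count will be visible. Protocol 2.0 treats 2 years as sufficient follow-up for QOL, so the problem sits mainly at one late time point. All of this stands, and it limits the point to a modest one. But N shows that the group shrank, not whether the change in the mean came from recovery or from who remained.

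The 30-month window is also fair: up to 68–94% could have a form counted as month 36. Forms are scheduled at 36 months, however, so actual coverage should lie between the nominal-date and window figures.

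Three stronger readings are tempting, and the documents do not support them.

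- **That the two means compare different patients.** The month-36 contributors are mainly a subset of the month-24 contributors, and each score is a within-patient change. Truncation by entry date biases the comparison only if outcome varies with entry date, and nothing in the documents shows that it does. Loss after progression or death is the more informative part.
- **That month-36 coverage may be as low as about 31%.** Dividing 304.7 person-years by 103 patients gives a mean of 35.5 months. With 24-month accrual, T is then 47.5 months and 40% reach month 36, but this assumes no EFS events. Multiplying by an event-free share of 77% then brings the events back. With events in both steps the range is 44–54%.
- **That the month-36 mean is shifted by a stated number of points.** Any such figure needs an assumed score difference between those who have and have not reached the visit. The documents supply none.

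**Conclusion.** The concern holds as a limitation of a descriptive secondary analysis. The plan reports only available-form means and SDs, and its cut-off rule and assessment schedule ensure that fewer patients contribute at month 36 than at month 24. The shares in Steps 2 to 4 are scenario results, not bounds. They rest on assumed uniform accrual over 24 to 36 months, a 2-month lag and exponential EFS, because no accrual dates are given. The direction is the same throughout, but neither the presence nor the size of bias in the scores can be derived from the documents. Primary EFS is not touched. The change is worth making because it is cheap and separates within-patient change from a change in who contributes.

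**What to change.** 1. Beside Tables 20 and 21, report month-24 and month-36 change in the patients who have both assessments. For FOIS and PSS-HN, which are ordinal, this is enough.
2. For FACT and MDADI, add to SAP 2.8.2.3 a supplementary repeated-measures mixed model: visit as a category, baseline score as covariate, all available forms, and model-based mean change with 95% CI at each time. State that it assumes data missing at random given observed scores, and that this is weakest after progression or death.
3. In SAP 2.8.2.2, count as expected only patients whose visit fell due before the cut-off. The current rule counts everyone alive at the time of assessment who has not withdrawn. It does not say how visits not yet due are handled, and it must be reconciled with the protocol's restriction of forms to the period before progression.

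Keep the raw means as description. Date the additions, since the SAP (V001, 2024-06-16) is later than the estimated cut-off of May 31, 2024. The cost is SAP wording, one standard model per scale and one extra table, all on data already collected.

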Table 10. Type of Distant metastasis free survival (DMFS) event and reason of censoring

Data set: All Eligible Patients

	Number of patients (%)	
	Total	N = ***
Patients who progressed	** (**)	
Distant metastasis	** (**)	
Death for any cause	** (**)	
Patients who were censored	** (**)	
Reason censored		
Lost to follow-up	** (**)	
Withdraw of consent	** (**)	
Not progressed	** (**)	
...		

Table 11. Subgroup analysis for EFS

Data set: All Eligible Patients (n = 99)					
Factor	Level	N	Number of events	2 year EFS rate (95% CI)	Hazard Ratio (95% CI)
Age	<= 65				
	>65				
Sex	Male				
	Female				
ECOG	1				
	0				
T stage	T1				
	T2				
	T3				
N stage	N0				
	N1				
Smoking history	No smoking ever				
	Ever smoked				
Chemotherapy	Yes				
	No				
Primary site	Base of tongue				
	Tonsil				
	Soft palate				

Table 12. Adverse Events

Data set: All treated patients							
		Number of patients (%) N=***					
		Worst grade					
		1	2	3	4	5	
Patients with any AE		** (**)	** (**)	** (**)	** (**)	** (**)	** (**)
Patients with AE within category							
Category 1 ⁽¹⁾		**(**)	**(**)	**(**)	**(**)	**(**)	**(**)
Event 1		**(**)	**(**)	**(**)	**(**)	**(**)	**(**)
Event 2		**(**)	**(**)	**(**)	**(**)	**(**)	**(**)
Event 3		**(**)	**(**)	**(**)	**(**)	**(**)	**(**)
...							
Category 2 ⁽¹⁾		**(**)	**(**)	**(**)	**(**)	**(**)	**(**)
Event 1		**(**)	**(**)	**(**)	**(**)	**(**)	**(**)
...							

Table 13. Serious adverse events

Data set: All treated patients							
Patients with any SAE	Number of patients (%) N=***					Any grade ** (**)	
	Worst grade						
	1	2	3	4	5		
** (**) ** (**) ** (**) ** (**) ** (**) ** (**) ** (**)							
Patients with AE within category							
Category 1 ⁽¹⁾	**(**) **(**) **(**) **(**) **(**) **(**) **(**)						
Event 1	**(**) **(**) **(**) **(**) **(**) **(**) **(**)						
Event 2	**(**) **(**) **(**) **(**) **(**) **(**) **(**)						
Event 3	**(**) **(**) **(**) **(**) **(**) **(**) **(**)						
...	**(**) **(**) **(**) **(**) **(**) **(**) **(**)						
Category 2 ⁽¹⁾	**(**) **(**) **(**) **(**) **(**) **(**) **(**)						
Event 1	**(**) **(**) **(**) **(**) **(**) **(**) **(**)						
...	**(**) **(**) **(**) **(**) **(**) **(**) **(**)						

Table 14. Drug Related Adverse Events**Table 14.1. Radiotherapy Related Adverse Events**

Data set: All treated patients						
	Number of patients (%) N=***					
	Worst grade					Any grade
	1	2	3	4	5	
Patients with any drug-related AE	** (**)	** (**)	** (**)	** (**)	** (**)	** (**)
Patients with AE within category						
Category 1 ⁽¹⁾	**(**)	**(**)	**(**)	**(**)	**(**)	**(**)
Event 1	**(**)	**(**)	**(**)	**(**)	**(**)	**(**)
Event 2	**(**)	**(**)	**(**)	**(**)	**(**)	**(**)
Event 3	**(**)	**(**)	**(**)	**(**)	**(**)	**(**)
...						
Category 2 ⁽¹⁾	**(**)	**(**)	**(**)	**(**)	**(**)	**(**)
Event 1	**(**)	**(**)	**(**)	**(**)	**(**)	**(**)
...						

Table 14.2. Chemotherapy Related Adverse Events

Data set: All treated patients						
	Number of patients (%) N=***					
	Worst grade					Any grade
	1	2	3	4	5	
Patients with any drug-related AE	** (**)	** (**)	** (**)	** (**)	** (**)	** (**)
Patients with AE within category						
Category 1 ⁽¹⁾	**(**)	**(**)	**(**)	**(**)	**(**)	**(**)
Event 1	**(**)	**(**)	**(**)	**(**)	**(**)	**(**)
Event 2	**(**)	**(**)	**(**)	**(**)	**(**)	**(**)
Event 3	**(**)	**(**)	**(**)	**(**)	**(**)	**(**)
...						
Category 2 ⁽¹⁾	**(**)	**(**)	**(**)	**(**)	**(**)	**(**)
Event 1	**(**)	**(**)	**(**)	**(**)	**(**)	**(**)
...						

Table 15. Drug Related Serious Adverse Events**Table 15.1. Radiotherapy Related Serious Adverse Events**

Data set: All treated patients

	Number of patients (%) N=***					
	Worst grade					Any grade
	1	2	3	4	5	
Patients with any drug-related SAE	** (**)	** (**)	** (**)	** (**)	** (**)	** (**)
Patients with SAE within category						
Category 1 ⁽¹⁾	**(**)	**(**)	**(**)	**(**)	**(**)	**(**)
Event 1	**(**)	**(**)	**(**)	**(**)	**(**)	**(**)
Event 2	**(**)	**(**)	**(**)	**(**)	**(**)	**(**)
Event 3	**(**)	**(**)	**(**)	**(**)	**(**)	**(**)
...						
Category 2 ⁽¹⁾	**(**)	**(**)	**(**)	**(**)	**(**)	**(**)
Event 1	**(**)	**(**)	**(**)	**(**)	**(**)	**(**)
...						

* Tables for cisplatin-related and radiotherapy-related SAE will also be presented.

WORST OVERALL GRADE 1 1 (1.0) (8.0)

* Adverse events graded according to CTCAE V5.0

Table 15.2. Chemotherapy Related Serious Adverse Events

Statistical Analysis Plan (SAP)

Doc. No.: HN.10
Version: V001
Date: 2024-06-16

Data set: All treated patients

	Number of patients (%)					
	Worst grade					Any grade
	1	2	3	4	5	
Patients with any drug-related SAE	** (**)	** (**)	** (**)	** (**)	** (**)	** (**)
Patients with SAE within category						
Category 1 ⁽¹⁾	**(**)	**(**)	**(**)	**(**)	**(**)	**(**)
Event 1	**(**)	**(**)	**(**)	**(**)	**(**)	**(**)
Event 2	**(**)	**(**)	**(**)	**(**)	**(**)	**(**)
Event 3	**(**)	**(**)	**(**)	**(**)	**(**)	**(**)
...						
Category 2 ⁽¹⁾	**(**)	**(**)	**(**)	**(**)	**(**)	**(**)
Event 1	**(**)	**(**)	**(**)	**(**)	**(**)	**(**)
...						

* Tables for cisplatin-related and radiotherapy-related SAE will also be presented.

WORST OVERALL GRADE 1 1 (1.0) (8.0)

* Adverse events graded according to CTCAE V5.0

Table 16. Number and (%) of patients off protocol treatment

Data set: All Treated Patients

	Radiotherapy (%)	Cisplatin (%)
	Total N = ***	Total N = ***
Off Treatment	** (**)	** (**)
Reason off treatment		
Reason 1	** (**)	** (**)
Reason 2	** (**)	** (**)
...		

Table 17. Death on trial (on protocol treatment or within 30 days off treatment)

Data set: All Treated Patients

	Number of patients (%)
	Total N = ***
Number of Patients who died during or within 30 days of last protocol treatment	** (**)
Cause of death	
Reason 1	** (**)
Reason 2	** (**)
...	

Table 18. Compliance (Received/Expected) with QoL assessment.**Table 18.1 FACT**

Data set: All Eligible Patients (n = 99)		
	Expected	Received (%)
Baseline		
Last week of Radiotherapy		
Follow up		
Month 3		
Month 6		
Month 12		
Month 24		
Month 36		

Table 18.2 MDADI

Data set: All Eligible Patients (n = 99)		
	Expected	Received (%)
Baseline		
Last week of Radiotherapy		
Follow up		
Month 3		

Month 6		
Month 12		
Month 24		
Month 36		

Table 18.3 FOIS

Data set: All Eligible Patients (n = 99)		
	Expected	Received (%)
Baseline		
Last week of Radiotherapy		
Follow up		
Month 3		
Month 6		
Month 12		
Month 24		
Month 36		

Table 18.2 PSS-HN

Data set: All Eligible Patients (n = 99)		
	Expected	Received (%)
Baseline		
Last week of Radiotherapy		
Follow up		
Month 3		
Month 6		
Month 12		
Month 24		
Month 36		

Table 19. Summary Baseline Scores.

	FACT-HN
Functional scales	
Physical	***
N	***
Mean	***

Statistical Analysis Plan (SAP)

Doc. No.: HN.10
 Version: V001
 Date: 2024-06-16

STD	***
Social/Family	
N	***
Mean	***
STD	***
Emotional	
N	***
Mean	***
STD	***
Functional	
N	***
Mean	***
STD	***
FACT-G total	
N	***
Mean	***
STD	***
FACT-HN	
N	***
Mean	***
STD	***
FACT-HN total	
N	***
Mean	***
STD	***
...	...
	MDADI
Global	
N	***
Mean	***
STD	***
Emotional	
N	***
Mean	***
STD	***
Physical	
N	***
Mean	***
STD	***
Functional	
N	***
Mean	***

STD	***
MDADI total	
N	***
Mean	***
STD	***

Table 20. Change score from baseline for scale/domain/item at each time period.

	Scale/domain/item
Scale/Domain/Item	
Last week of RT	
N	***
Mean	***
STD	***
3 months post RT	
N	***
Mean	***
STD	
6 months post RT	
N	***
Mean	***
STD	
...	
N	***
Mean	***
STD	

* Table will be provided for each scale/domain/item.

Table 21. Change score from baseline for FOIS/PSS-HN at each time period.

	Scale/domain/item
Scale/Domain/Item	
Last week of RT	
N	***
Mean	***
STD	***
3 months post RT	
N	***
Mean	***
STD	

Statistical Analysis Plan (SAP)

Doc. No.: HN.10
Version: V001
Date: 2024-06-16

6 months post RT	
N	***
Mean	***
STD	
...	
N	***
Mean	***
STD	

* Table will be provided for each scale/domain/item.
